8.2 VISIT 1 (INFUSION 1 OF EMAPALUMAB; SD0)

The following assessments are to be performed pre-infusion at Visit 1 (SD0):

Clinical Assessment:

- Vital signs, including body temperature, heart rate, blood pressure, and oxygen saturation
- Physical examination, including as a minimum, weight, spleen and liver size (by abdominal palpation), and neurological examination

Laboratory:

- CBC with differential count (including large unstained cells count, whenever performed as routine)
- Coagulation tests: activated partial thromboplastin time and/or ratio, prothrombin time and/or INR, D-dimers and fibrinogen
- Biochemistry: glucose, ferritin, CRP, liver function (AST, ALT, γGT, LDH, ALP, bilirubin), renal function (albumin, creatinine and urea) and triglycerides (fasting whenever possible)
- Urinalysis: glucose, blood, protein and/or albumin, leucocytes, ketones, pH and specific gravity

Imaging

 Abdominal ultrasound (spleen longitudinal measure), if 2 weeks or longer elapsed between the screening visit and SD0

Safety:

 Recording of any AEs occurred since last screening visit or prior to infusion

PK:

Emapalumab serum concentrations

Study NI-0501-09 NI-0501 in Primary HLH Page 51 of 92

PD: CXCL9, CXCL10, sCD25, total IFNy

Immunogenicity: ■ ADAs

IMP Handling: • Preparation, dispensing, and accountability

The infusion will be administered over a period of 1 to 2 hours depending on the volume to be infused.

Blood pressure, heart rate and oxygen saturation (pulse oximetry) will be collected every 15 minutes during and until the end of the infusion.

The following assessments are to be performed post-infusion:

Vital sign assessment: • Heart rate, oxygen saturation, blood pressure and temperature at

the end of the infusion, 1 hour and 2 hours after completion of

emapalumab infusion

PK: ■ Emapalumab serum concentration.

8.3 VISIT 2 (INFUSION 2 OF EMAPALUMAB; SD3)

The following assessments are to be performed pre-infusion at Visit 2 (SD3):

Clinical Assessment: • Vital signs, including body temperature, heart rate, blood pressure,

and oxygen saturation

Physical examination, including as a minimum, weight, spleen and

liver size (by abdominal palpation), and neurological examination

Laboratory:

• CBC with differential count (including large unstained cells count,

whenever performed as routine)

Coagulation tests: activated partial thromboplastin time and/or ratio,

prothrombin time and/or INR, D-dimers, and fibrinogen

 Biochemistry: glucose, ferritin, CRP, liver function (AST, ALT, γGT, LDH, ALP, bilirubin), renal function (albumin, creatinine and urea) and

triglycerides (fasting whenever possible)

Safety: • Recording of any AEs occurred since start of first infusion

PK: Emapalumab serum concentrations

PD: ■ CXCL9, CXCL10, sCD25, total IFNy

IMP Handling: • Preparation, dispensing, and accountability

The infusion will be administered over a period of 1 to 2 hours depending on the volume to be infused.

The second infusion must be administered on SD3.

During the infusion, monitoring of heart rate and oxygen saturation will be performed, with recording of values at 30 minutes after the beginning of the infusion. If this is the first infusion at an increased dose of emapalumab, and/or patient has experienced an infusion-related reaction, blood pressure, heart rate and oxygen saturation are to be collected every 15 minutes during and until the end of the infusion.

The following assessments are to be performed post-infusion:

Study NI-0501-09 NI-0501 in Primary HLH Page 52 of 92

Vital sign assessment:

 Heart rate, oxygen saturation, blood pressure and temperature at the end of the infusion, 1 hour and 2 hours after completion of emapalumab infusion

PK:

Emapalumab serum concentration.

8.4 VISIT 3 AND ONWARDS (INFUSION 3 OF EMAPALUMAB AND ONWARDS)

The following assessments are to be performed pre-infusion at all visits from Visit 3 onwards, unless specified differently:

Clinical Assessment:

- Vital signs, including body temperature, heart rate, blood pressure, and oxygen saturation
- Physical examination, including as a minimum, weight, spleen and liver size (by abdominal palpation), and neurological examination
- Assessment of clinical response every 2 weeks

Search for infections:

- TB by PCR (every 4 weeks)
- Infection search & monitoring in case of suspicion of infection or if there is an active infection at screening/baseline to monitor evolution of viral load and positivity for an identified pathogen
- Atypical mycobacteria, Histoplasma capsulatum, Shigella, Salmonella, Campylobacter, Leishmania - if an infection is suspected

Laboratory:

- CBC with differential count (including large unstained cells count, whenever performed as routine)
- Coagulation tests: activated partial thromboplastin time and/or ratio, prothrombin time and/or INR, D-dimers and fibrinogen
- Biochemistry: glucose, ferritin, CRP, liver function (AST, ALT, γGT, LDH, ALP, bilirubin), renal function (albumin, creatinine and urea) and triglycerides (fasting whenever possible)

Imaging:

- Abdominal ultrasound with spleen longitudinal measure (every 2 weeks during emapalumab treatment)
- Chest X-ray in case of clinical suspicion of pulmonary infection or to monitor existing abnormalities

Safety:

Recording of any AEs occurred since last visit

PK:

 Emapalumab serum concentration (every other infusion starting from Visit 3)

PD:

 CXCL9, CXCL10, sCD25, total IFNγ (every other infusion starting from Visit 3)

Immunogenicity:

ADAs (only at Week 4, together with a PK sample)

IMP Handling:

Preparation, dispensing, and accountability

The infusion will be administered over a period of 1 to 2 hours twice a week (not more than 4 days apart). Monitoring of heart rate and oxygen saturation will be performed, with recording of values at 30 minutes after the beginning of the infusion. If this is the first infusion at an increased dose of emapalumab, and/or

Study NI-0501-09 NI-0501 in Primary HLH Page 53 of 92

patient has experienced an infusion-related reaction, blood pressure, heart rate and oxygen saturation are to be collected every 15 minutes during and until the end of the infusion.

The following assessments are to be performed post-infusion at Visit 3 and onwards:

Vital sign assessment:

 Heart rate, oxygen saturation, blood pressure and temperature at the end of the infusion, 1 hour and 2 hours after completion of emapalumab infusion

PK:

 Emapalumab serum concentration (every other infusion starting from Visit 3)

Clinical Assessment:

 QOL questionnaire - PedsQL[™], Pediatric Quality of Life Inventory[™] (at Visit 3 only)

During treatment, emapalumab and biomarker concentrations may be measured in other matrices, such as CSF or BAL, if samples obtained in procedures which are performed for diagnostic/therapeutic purposes can also be available for these exploratory investigations, and if clinically indicated.

8.5 WEEK 8 ASSESSMENT VISIT (3 DAYS AFTER WEEK 8 INFUSION) AND END OF TREATMENT VISIT (3 DAYS AFTER LAST EMAPALUMAB INFUSION)

These visits will include a full patient's assessment.

The Week 8 Assessment Visit will be performed 3 (± 1) days after the last Week 8 emapalumab infusion. If treatment with emapalumab is completed before Week 8, only an EOT visit will be performed 3 (± 1) days after the last infusion.

For patients continuing treatment beyond Week 8, an EOT visit will be conducted 3 (± 1) days after the last emapalumab infusion.

The following assessments are to be performed at the Week 8 Assessment Visit and at the EOT Visit:

Clinical Assessment:

- Vital signs, including body temperature, heart rate, blood pressure, and oxygen saturation
- Physical examination, including as a minimum, weight, spleen and liver size (by abdominal palpation), and neurological examination
- Assessment of clinical response
- QOL questionnaires PedsQL[™], Pediatric Quality of Life Inventory[™],
 BASES (BASES only at EoT and if HSCT is planned)

Procedure:

ECG (only at EOT)

Search for infections:

- TB by PCR (if not performed within the last 4 weeks)
- Infection search & monitoring in case of suspicion of infection or if there is an active infection at screening/baseline to monitor evolution of viral load and positivity for an identified pathogenAtypical mycobacteria, Histoplasma Capsulatum, Shigella, Salmonella, Campylobacter, Leishmania – only if an infection is suspected

Study NI-0501-09 NI-0501 in Primary HLH Page 54 of 92

Laboratory:

 CBC with differential count (including large unstained cells count, whenever performed as routine)

- Coagulation tests: activated partial thromboplastin time and/or ratio, prothrombin time and/or INR, D-dimers, and fibrinogen
- Biochemistry: glucose, ferritin, CRP, liver function (AST, ALT, γGT, LDH, ALP, bilirubin), renal function (albumin, creatinine and urea) and triglycerides (fasting whenever possible)
- Pregnancy test, if applicable (only EOT)
- Urinalysis: glucose, blood, protein and/or albumin, leucocytes, ketones, pH (only EOT), gravity

Imaging: • Abdominal ultrasound with spleen longitudinal measure

Safety: Recording of any AEs occurred since last visit

PK: Emapalumab serum concentration

PD: ■ CXCL9, CXCL10, sCD25, total IFNy

Immunogenicity: ■ ADAs

IMP Handling: Preparation, dispensing, and accountability (week 8 only)

If emapalumab treatment is continued, and **Week 8 Assessment Visit** is performed on the same day of the subsequent infusion, the infusion will be administered over a period of 1 to 2 hours. Monitoring of heart rate and oxygen saturation will be performed, with recording of values at 30 minutes after the beginning of the infusion. If this is the first infusion at an increased dose of emapalumab, and/or patient has experienced an infusion-related reaction, blood pressure, heart rate and oxygen saturation are to be collected every 15 minutes during and until the end of the infusion.

The following assessments will be performed post-infusion:

Vital sign assessment:

 Heart rate, oxygen saturation, blood pressure and temperature at the end of the infusion, 1 hour and 2 hours after completion of emapalumab infusion

PK: ■ Emapalumab serum concentration

8.6 FOLLOW-UP PERIOD

A long-term follow-up will be conducted after the completion (or premature discontinuation) of emapalumab treatment, until 1 year after either HSCT or last emapalumab infusion (if HSCT is not performed). For patients not planned to receive HSCT, the long-term follow-up period will be conducted according to the same schedule of post-HSCT follow-up.

8.6.1 Follow-Up Pre-HSCT: Pre-Conditioning Visit

The following assessments have to be performed before starting the administration of conditioning agents for HSCT. This visit can be combined with the EOT visit, if the visits are not more than 2 days apart.

If the pre-conditioning and EOT visits are not combined, the following assessments are to be performed:

Study NI-0501-09 NI-0501 in Primary HLH Page 55 of 92

Clinical Assessment:

- Vital signs, including body temperature, heart rate, blood pressure, and oxygen saturation
- Physical examination, including as a minimum, spleen and liver size (by abdominal palpation), height/length and neurological examination
- Survival

Laboratory:

- CBC with differential count (including large unstained cells count, whenever performed as routine)
- Coagulation tests: activated partial thromboplastin time and/or ratio, prothrombin time and/or INR, D-dimers, and fibrinogen
- Biochemistry: glucose, ferritin, CRP, liver function (AST, ALT, γGT, LDH, ALP, bilirubin), renal function (albumin, creatinine and urea) and triglycerides (fasting whenever possible)
- Urinalysis: glucose, blood, protein, leucocytes, ketones, pH, gravity

Imaging:

- Abdominal ultrasound with spleen longitudinal measure
- Chest X-ray. Other imaging modalities (e.g. CT) performed as part of pre-transplant work-up are also acceptable.

Safety:

Recording of any AEs occurred since last visit

PK:

- Emapalumab serum concentration
- PD: CXCL9, CXCL10, sCD25, total IFNγ.

8.6.2 Follow-Up Post-HSCT (or After Last Emapalumab Infusion)

The following assessments will be performed at weekly visits after either HSCT or last emapalumab infusion (as applicable) until Day 30, and subsequently at Day 60, Day 100, and Month 6:

(In addition to the below, in patients undergoing HSCT, PK/PD samples will be collected at Day 3 post-transplant).

Clinical Assessment:

- Vital signs, including body temperature, heart rate, blood pressure, and oxygen saturation
- Physical examination, including as a minimum, spleen and liver size (by abdominal palpation), height/length (at 6 month visit only) and neurological examination
- Post HSCT outcome, if applicable
- Survival
- QOL questionnaires PedsQL[™], Pediatric Quality of Life Inventory[™] and BASES if HSCT is performed (at Day 30, Day 100 and Month 6 visits)

Laboratory:

- CBC with differential count (including large unstained cells count, whenever performed as routine)
- Coagulation tests: activated partial thromboplastin time and/or ratio, prothrombin time and/or INR, D-dimers, and fibrinogen

Study NI-0501-09 NI-0501 in Primary HLH Page 56 of 92

- Biochemistry: glucose, ferritin, CRP, liver function (AST, ALT, γGT, LDH, ALP, bilirubin), renal function (albumin, creatinine and urea) and triglycerides (fasting whenever possible)
- Urinalysis: glucose, blood, protein and/or albumin, leucocytes, ketones, pH, gravity

Search for infections:

- TB by PCR in any relevant specimen, as clinically indicated, at minimum at D+30, D+60, D+100, 6 month and 1 year/WD visits; until serum levels of emapalumab are no longer detectable
- Infection search & monitoring according to the patient's clinical presentation – in case of suspicion of infection

Imaging:

- Chest X-ray in case of clinical suspicion of pulmonary infection or to monitor existing abnormalities
- Abdominal ultrasound with spleen longitudinal measure (at Day 100 visit only)

Safety:

 Recording of any AEs occurred since last visit until serum levels of emapalumab are no longer detectable. After elimination of emapalumab only SAEs will be reported.

PK:

 Emapalumab concentrations (if serum levels of emapalumab were still measurable at the previous visit). Also at D+3 after HSCT, if performed

PD:

 CXCL9, CXCL10, sCD25, total IFNy (if serum levels of emapalumab were still measurable at the previous visit; then only if clinically indicated). Also at D+3 after HSCT, if performed

Immunogenicity:

Assessment for ADAs (at Day 100 visit only)

8.6.3 End of Study: 1-Year Visit Post-HSCT (or After Last Emapalumab Infusion)/Withdrawal Visit

This visit represents the last visit of the study. The following assessments will be performed:

Clinical Assessment:

- Vital signs, including body temperature, heart rate, blood pressure, and oxygen saturation
- Physical examination, including as a minimum, spleen and liver size (by abdominal palpation), and neurological examination
- Post HSCT outcome, if applicable
- Survival
- QOL questionnaires PedsQL™, Pediatric Quality of Life Inventory™ and BASES if HSCT is performed

Laboratory:

- CBC with differential (including large unstained cells count, whenever performed as routine)
- Coagulation tests: activated partial thromboplastin time and/or ratio, prothrombin time and/or INR, D-dimers, and fibrinogen

Study NI-0501-09 NI-0501 in Primary HLH Page 57 of 92

•	Biochemistry: glucose, ferritin, CRP, liver function (AST, ALT, γGT,
	LDH, ALP, bilirubin), renal function (albumin, creatinine and urea)
	and triglycerides (fasting whenever possible)

Urinalysis: glucose, blood, protein, leucocytes, ketones, pH, gravity

Search for infections:

PK:

- TB by PCR in any relevant specimen (if serum levels of emapalumab were still measurable at the previous visit)
- Infection search & monitoring according to the patient's clinical presentation – in case of suspicion of infection

Imaging: • Abdominal ultrasound with spleen longitudinal measure

Safety:

Recording of any AEs occurred since last visit until serum levels of emapalumab are no longer detectable. After elimination of

emapalumab only SAEs will be reported.

Emapalumab concentrations (if serum levels of emapalumab were

still measurable at the previous visit)

PD: CXCL9, CXCL10, sCD25, total IFNγ (if serum levels of emapalumab

were still measurable at the previous visit, or if clinically indicated)

Immunogenicity: • Assessment for ADAs

8.7 ASSESSMENTS IN CASE OF UNPLANNED/UNSCHEDULED VISITS

Unplanned visits may occur should the patient need to be assessed or treated for any clinical condition that arises during the study. This includes the evaluation and follow-up of AEs and SAEs.

8.8 UNPLANNED ASSESSMENTS

Additional PK/PD samples may be required to better characterize the PK/PD profile and/or for safety reasons. The number of additional samples taken will depend on the weight and health status of the patient, and will be taken only if the amount of blood required is acceptable in the context of the EMA guideline and USA pediatric recommendations (see Section 8).

9 SAFETY MONITORING

9.1 DESCRIPTION OF SAFETY PARAMETERS

Evaluation of emapalumab tolerability and safety will be based on the following parameters:

- AEs (serious and non-serious)
- Laboratory parameters, including:
 - CBC with differential counts
 - Coagulation tests (activated partial thromboplastin time and/or ratio, prothrombin time and/or INR), d-Dimer, and fibrinogen
 - Biochemistry: glucose, ferritin, CRP, liver function (AST, ALT, γGT, LDH, ALP, bilirubin), renal function (albumin, creatinine and urea) and triglycerides (fasting whenever possible)

- TB PCR results
- Vital signs: body temperature, heart rate, blood pressure, oxygen saturation
- If present at baseline or emerging during treatment, the following parameters will be collected until resolution:
 - evolution of viral load and positivity for an identified pathogen(frequency of collection driven by site local practices).

9.2 RECORDING AND REPORTING SAFETY PARAMETERS

9.2.1 Adverse Events

Adverse events (AEs) are defined as any undesirable experience occurring to a patient during the study, whether or not considered related to the IMP. All AEs occurring during the study, i.e., from the date of ICF signature up to and including the end-of-study visit must be recorded on the AE page of the electronic CRF (eCRF). Once emapalumab serum levels are no longer detectable, only serious AEs (SAEs) will be recorded on the AE page of the eCRF.

Medical conditions present at Screening or diagnosed at the Screening visit will be recorded in the medical history section of the eCRF.

An AE which occurs between the Screening visit and the start of first IMP administration will be considered as a pre-treatment AE.

Any AE that occurs after the start of first IMP administration will be considered as a Treatment Emergent Adverse Event (TEAE), including the specific situations described below. AEs are collected after signing of ICF up to Study Completion or until serum levels of emapalumab are no longer detectable (whichever occurs first). After elimination of emapalumab only SAEs will be reported.

Should a pre-existing medical condition worsen (clinically significant change in intensity or frequency), it must be recorded as an AE in the eCRF and, depending on the time of its occurrence, will be considered as a pre-treatment AE or a TEAE. Should a medical condition recorded as a pre-treatment AE worsen after start of IMP administration, it will be recorded in the eCRF as a separate TEAE, specifying `Worsening of xxx`.

For all AEs, the following will be assessed and recorded: onset and end dates (and -when relevant- time), intensity, seriousness, relationship to IMP, action taken regarding IMP, any treatment received, and outcome.

Intensity of AEs will be graded on a three-points scale (mild, moderate, severe) using the modified World Health Organization (WHO) toxicity scale (Grade 3 and 4 are considered to be the severe grade). If AE severity is not mentioned in the scale, assessment will be made using the following definitions:

- Mild: Discomfort noticed but no disruption of normal activity
- Moderate: Discomfort sufficient to reduce or affect normal daily activity
- Severe: Inability to work or perform normal daily activity

For a given AE, the assessment of its intensity should reflect the highest grade (on the three-point scale mentioned above) reported during its course (except when the intensity of a pre-treatment AE increases after treatment initiation, as indicated above).

The relationship of AEs to the IMP will be assessed by the Investigator using a "Yes/No" classification. A "Yes" relationship infers that there is a reasonable suspected causal relationship to the IMP. The

Study NI-0501-09 NI-0501 in Primary HLH Page 59 of 92

expression "reasonable causal relationship" is meant to convey that there are facts, evidence or arguments to suggest a causal relationship. In this study, emapalumab is the only IMP.

Specific situations:

- Common HLH signs and symptoms (e.g., anemia, neutropenia, thrombocytopenia, pancytopenia, splenomegaly, hepatomegaly) will not be reported as separate AEs unless clearly attributed to a cause different from HLH, and the verbatim term should indicate the cause.
- If changes in the above mentioned HLH signs and symptoms indicate HLH worsening or reactivation, worsening or reactivation will be reported as an AE.
- Fever will only be reported when not linked to an identified cause with the highest temperature considered during the period. If it is a recurrent fever it can be entered as intermittent fever with no need to specify the temperature (the intensity should be a reflection of the highest temperature observed). If fever is considered as a sign of a confirmed infection or of HLH worsening or reactivation, only the diagnosis should be reported as an AE, and not `fever`.
- Viral load positivity, in particular for EBV, CMV and adenovirus, and evolution will be collected on a dedicated eCRF module.
- Active infections will be reported as AEs, indicating whether constituting a primary infection or a reactivation (whenever possible). Pathogen positivity and evolution will be collected in a dedicated eCRF module.
- Expected effects of conditioning (i.e., pancytopenia during conditioning and until engraftment) will not be reported.

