Abbreviations: ADAs, anti-drug antibodies; AE, adverse event; ALP, alkaline phosphatase; ALT, alanine transaminase, aPTT, activated partial thromboplastin time; AST, aspartate transaminase; CBC, complete blood count; cm, centimeter; CMV, cytomegalovirus; CRP, C-reactive protein; D, day; EBV, Epstein-Barr virus; EOT, end of treatment; yGT, gamma glutamyl transferase; HSCT, hematopoietic stem cell transplantation; ICF, informed consent form; IFNy, interferon gamma; INR, International normalized ratio; LDH, lactate dehydrogenase; LUC, large unstained cells; mo, month; PD, pharmacodynamic; PK, pharmacokinetic; PT, prothrombin time; QOL, quality of life; SAE, serious adverse event; TB, tuberculosis; US, ultrasound; UV, unscheduled visit; WD, withdrawal visit; wk, week; yr, year CBC: white blood cells and differential, red blood cells, hemoglobin, hematocrit, platelets, LUC (as available). Coagulation: aPTT (time and/or ratio), PT and/or INR, d-Dimers, fibrinogen. Biochemistry: glucose, CRP, ferritin, triglycerides, liver (AST, ALT, yGT, LDH, ALP, bilirubin) and renal function (albumin, creatinine and urea). Urinalysis: glucose, blood, protein and/or albumin, leukocytes, ketones, pH, gravity

^{*} Follow-up pre-HSCT: if HSCT is not planned, patient will directly follow the Schedule of Assessment indicated for Follow-up after last emapalumab infusion

^b **EOT**: indicated as reference only, refer to Table 1

Fre Conditioning visit: may be combined with EOT visit (if not more than 2 days apart). The EOT schedule of assessments has to be applied

d Allowed time-windows: a ±2 day window is allowed until D+30 visit. A ±1 week window is allowed for D+60 and D+100 visits. A ±4 week window is allowed for 6-mo and 1-yr visits

e WD (Withdrawal visit): assessments as indicated for last study visit are to be performed in case of premature study discontinuation

f UV (Unscheduled visit): assessments to be performed as clinically indicated

F Physical examination: includes as a minimum: spleen and liver size (by abdominal palpation), height/length (at Pre-Conditioning and 6 month visit only) and neurological examination

h Post-HSCT outcome: applies to patients who undergo HSCT. Includes engraftment rate, donor chimerism achieved (as available), incidence of acute and chronic graft versus host disease

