3.4 FOLLOW-UP PERIOD

After treatment completion or treatment discontinuation (for any reason), patients will continue in the study for long-term follow-up until 1 year after either HSCT or last emapalumab infusion (if HSCT is not performed).

Study NI-0501-09 NI-0501 in Primary HLH Page 31 of 92

If patient experiences HLH reactivation during the follow-up period, patient may be re-treated with emapalumab, upon discussion with Sponsor. Re-treated patient will follow the same schedule of assessments as applicable during initial treatment (i.e., starting from Visit 1), and will enter follow-up period after completion of re-treatment.

If the patient is unable to return to the site for all follow-up visits, every effort should be made to schedule visits until emapalumab is no longer detectable in the blood.

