9.2.2 Serious Adverse Events

Any AE is considered "serious" if it:

- results in death (note: death is an outcome, not an event);
- is life-threatening; (note: the term "life-threatening" refers to an event in which the patient was at immediate risk of death at the time of the event; it does not refer to an event which could hypothetically have caused a death had it been more severe);
- requires in-patient hospitalization or prolongs an existing hospitalization;
- results in persistent or significant disability/incapacity;
- is a congenital anomaly/birth defect;
- is an important medical event, i.e., refers to an event that may not result in death, be lifethreatening, or require hospitalization but may be considered as serious when, based upon appropriate medical judgment, may jeopardize the patient, and may require medical or surgical intervention to prevent one of the outcomes listed in this definition above.

The following reasons for hospitalization are exempted from being reported:

- elective hospitalizations for surgical procedures that are a result of a patient's pre-existing condition(s) which have not worsened during the study;
- hospitalization requested for emapalumab infusion and study visits (including a possible hospital stay overnight, if due to logistic convenience);
- post-HSCT hospitalization as a measure of caution in this fragile population, to investigate a clinical sign or symptom (e.g. fever), provided that the hospital stay has a duration of less than 72 hours and does not result in any confirmed new diagnosis (e.g., negative search of infection in

presence of fever which resolves with symptomatic measures); in this case the sign will be recorded as an AE.

For the initial SAE report, the Investigator should report all available case details concerning the patient and the event, using the Swedish Orphan Biovitrum AG SAE reporting form within 24 hours of awareness.

Swedish Orphan Biovitrum AG contact information for SAE reporting:

E-mail: [contact]

Relevant follow-up information on SAEs should be forwarded to Swedish Orphan Biovitrum AG as soon as it becomes available. In addition, the Investigator must be available to answer without delay any request for follow-up information or questions that Swedish Orphan Biovitrum AG may have regarding the SAE.

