• Survival to HSCT, defined as the time from the date of first dose to the date of death. Patients who receive a HSCT will be censored at that date. Patients who did not receive HSCT will be censored at date of last contact. The analysis start and end dates and the censoring rules are described in the following scheme:

Table 9: Survival to HSCT

Situation	Outcome (event or censored)	Analysis start date	Analysis end date
No assessments after first infusion	Censored	Start of treatment	Start of treatment + 1
Death for any cause	Event	Start of treatment	Death
Alive at HSCT	Censored	Start of treatment	HSCT date
Alive without having received HSCT	Censored	Start of treatment	Last known alive date

Protocol Number NI-0501-09 PCN Number 176784

[figure not shown]
Statistical Analysis Plan, Sponsor Sobi AG

• Survival post HSCT, defined as the time from date of HSCT to the date of death. Patients without an event will be censored at date of last contact. Patients who do not proceed to HSCT will be excluded from this analysis. The analysis start and end dates and the censoring rules are described in the following scheme:

Table 10: Survival post HSCT

Situation	Outcome (event or censored)	Analysis start date	Analysis end date
Death for any cause	Event	Date of HSCT	Death
Alive at the end of the observation period* Censored Date of HSCT Last known alive date			
* end of study, or any time during follow-up period (including withdrawal of consent)			

- HLH Reactivation = any adverse event in the following preferred term (PT) (PT code):
 - Condition Aggravated (10010264)
- Graft failure = any adverse event in at least one of the following PTs (PT code):
 - Transplant failure (10060872)
 - Engraft failure (10068081)
 - Bone marrow transplant rejection (10048396)
 - Transplant rejection (10044439)
 - Complications of bone marrow transplant (10010162)
 - Graft loss (10048748)
- Event-free survival = time from HSCT to date of (whichever occurs first): death from any cause, graft failure, HLH reactivation. The analysis start and end dates and the censoring rules are described in the following scheme:

Situation	Outcome (event or censored)	Analysis start date	Analysis end date	
At least one event, i.e. graft failure, HLH reactivation, death for any cause	Event	Date of HSCT	Date of first event	
None of the events at the end of the observation period*	Censored	Date of HSCT	Last known alive	

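### Event-free survival counts graft failure and HLH reactivation only from AE records up to 1 year after HSCT, but AE recording narrows to serious events once emapalumab is undetectable, so EFS may be overstated by an unknown and possibly small amount

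*Protocol*

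**What the plan says.** **Endpoint (SAP 6.1.9.4).** "Event-free survival = time from HSCT to date of (whichever occurs first): death from any cause, graft failure, HLH reactivation". The two non-fatal components come only from coded AEs, with no condition on seriousness. For graft failure the rule reads "Graft failure = any adverse event in at least one of the following PTs (PT code", followed by six terms. For reactivation it reads "HLH Reactivation = any adverse event in the following preferred term (PT) (PT code", followed by the single term Condition Aggravated. In Table 11, a patient with "None of the events at the end of the observation period" is censored at the last known alive date.

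**Follow-up (Protocol 3.4).** After treatment, "patients will continue in the study for long-term follow-up until 1 year after either HSCT or last emapalumab infusion".

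**AE recording (Protocol 9.2.1).** "Once emapalumab serum levels are no longer detectable, only serious AEs (SAEs) will be recorded on the AE page of the eCRF". The same restriction appears in the synopsis, in sections 8.6.2 and 8.6.3, and in Table 2 footnote n. The sentence just before it in 9.2.1, however, requires all AEs to be recorded through the end-of-study visit. The synopsis and the specific situations in 9.2.1 also say that reactivation or worsening of HLH is reported as an AE. They do not say whether this continues after elimination.

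**Other data.** Table 2 schedules a post-HSCT outcome assessment at the follow-up visits to 1 year. Footnote h describes its content: "Includes engraftment rate, donor chimerism achieved (as available), incidence of acute and chronic graft versus host disease". In the SAP these data appear as Listing 16.2.6.6 and do not enter the EFS derivation.

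**The concern.** The endpoint counts any AE over a fixed year, but the data collection guarantees any AE for only part of that year. The change-over depends on each patient's drug level and not on the EFS window. Because censoring is at last known alive and not at the end of full AE collection, a late event that nobody records becomes event-free time. Missing a first event can only raise the EFS curve.

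EFS is a secondary endpoint and bears on the objective of gathering long-term outcome evidence. With few transplanted patients, a single missed event would be visible in the 1-year estimate.

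**Working it through.** The plan gives no EFS rate, event count or power, so there is no stated figure to reproduce. The check is a comparison of the texts, followed by an illustration of size.

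**Step 1. Can an event of interest be non-serious?** Protocol 9.2.2 defines serious broadly: death, threat to life, admission or prolonged admission, disability, birth defect, or an important medical event. The reactivation definition in the footnote to inclusion criterion 4 (Protocol 4.1.1), written for eligibility, can be met by laboratory values alone: two parameters that become abnormal and worsen by more than 30% on two assessments at most a week apart. That requires no admission and no threat to life. Such a case is serious only if the investigator or sponsor judges it an important medical event. Admission for an emapalumab infusion, as in re-treatment, is exempt from SAE reporting.

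**Step 2. Is there another route into EFS?**

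| Component | Other data collected to 1 year | Used for EFS? |
|---|---|---|
| Graft failure | Engraftment; donor chimerism as available | No, listed only |
| Reactivation | Laboratory values; re-treatment, tabulated under SAP 7.1 | No |

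Table 2 has no dedicated reactivation or clinical-response item in follow-up, so the gap is wider for reactivation.

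**Step 3. Size.** Let q be the true proportion of transplanted patients whose first event is non-fatal, L the share of those events that fall after emapalumab is undetectable, and s the share of those that are non-serious. Ignoring censoring, the excess in 1-year EFS is q × L × s. None of the three values is in the documents; all are assumed.

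With q = 20%, L = 50% and 28 transplanted patients (also assumed):

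| s | Excess (percentage points) | Expected missed events (28 × excess) |
|---|---|---|
| 0% | 0 | 0 |
| 5% | 0.20 × 0.50 × 0.05 = 0.5 | 0.14 |
| 10% | 0.20 × 0.50 × 0.10 = 1.0 | 0.28 |
| 25% | 0.20 × 0.50 × 0.25 = 2.5 | 0.7 |
| 50% | 0.20 × 0.50 × 0.50 = 5.0 | 1.4 |

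At s = 10%, the chance of missing at least one event is 1 − 0.99^28 = 24.5%.

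Over q = 10–30%, L = 25–75% and s = 0–50%, the excess runs from 0 to 0.30 × 0.75 × 0.50 = 11.25 points. The formula errs high where a missed event is followed within the year by death or a recorded serious event, because that patient then counts as an event, only later.

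**The case against.** **Seriousness may close the gap.** Reactivation or graft loss after transplant will often mean admission or a threat to life. If every such event is reported as serious, nothing is missed. This stands as a limit on size. It does not remove the mismatch, because the important-medical-event category is a judgement.

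**Reactivation may still be reportable.** The synopsis places reactivation among the exceptions to the time-limited AE rule and gives no end date. This makes capture ambiguous and not plainly absent. The synopsis also repeats the SAE-only rule, and nothing comparable covers graft failure.

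**The information is not wholly lost.** Engraftment, chimerism, blood counts, fibrinogen, ferritin and re-treatment are in the database. This is correct, and it is why the fix is cheap, but none of them feeds EFS as defined.

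**Bias may run the other way.** Condition Aggravated and Complications of bone marrow transplant are broad terms and may count things that are neither reactivation nor graft failure. The net direction is therefore uncertain.

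Three stronger readings are tempting but unsupported:

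- A reader might infer that the exemption from SAE reporting for post-HSCT stays under 72 hours loses EFS events. It covers signs without a confirmed new diagnosis, such as fever, for which "in this case the sign will be recorded as an AE". Such a sign would not code to an EFS term. Whether a reactivation counts as a new diagnosis is not stated.
- A reader might infer that capture depends on disease activity, since Protocol 5.2 says clearance rises with IFNγ production. Dose also follows disease activity (Protocol 5.3), so the direction of any link with time to undetectability cannot be derived.
- A reader might take the share of the year after an assumed clearance date as the size of the loss, for instance (365 − 100)/365 = 73% for D+100. That is a share of calendar time and not of events. The documents give no elimination time, and the blood-volume calculation in Protocol section 8 allows for a drug detectable throughout follow-up.

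**Conclusion.** The mismatch between the EFS definition and AE recording is established by the text. Its effect is possible and not demonstrated: EFS may be overstated by an unknown and possibly small amount. The mechanism needs at least one first event that occurs after elimination and is both judged non-serious and left unrecorded. A reader might conclude that events are lost and EFS is overstated. The documents do not show that, for the reasons given on seriousness, ambiguous reactivation reporting and broad coding terms.

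Under the assumptions shown, the excess is 0 to 1 point in the middle scenario (q = 20%, L = 50%) if at most 10% of late events are non-serious, and 11.25 points at the extreme. It is zero if all late events are reported as serious or if emapalumab stays detectable all year. EFS is descriptive and carries no test, so the primary conclusion does not depend on this. The point still merits correction, because the plan followed as written can count a late reactivation as event-free time.

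**What to change.** **Protocol 9.2.1 and Table 2 footnote n.** State that HLH reactivation or worsening and graft failure or rejection are recorded to the 1-year visit regardless of seriousness and emapalumab level. Reconcile the two adjoining sentences in 9.2.1 on how long AEs are recorded, and align the synopsis.

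**SAP 6.1.9.4.** Also use the post-HSCT outcome data (engraftment, and chimerism as available) to identify graft failure. Footnote h shows no event date, so use the visit or assessment date where none is captured. Count re-treatment for a reactivation in follow-up as a reactivation event.

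**Data already collected.** Add an EFS sensitivity analysis that censors the non-fatal components at the end of full AE collection, and state in advance how that date is derived and how later deaths are handled. Later deaths remain visible in the analysis of survival post HSCT.

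**Cost.** One recording instruction with matching eCRF guidance, additional sources in a derivation, and one extra analysis. No new visit or test is needed. The downside is a few more AE entries and possibly a slightly lower EFS.
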